8.2.4. Annualized Incidence Rate of VOCs

Annualized incidence rate of VOC will be calculated for each treatment group (total number of events)/(total subject-years on treatment) and associated 95% exact Poisson confidence limits will be reported. For any subjects that initiating HU postbaseline, data up to the time of HU initiation will be used. The incidence rate ratio (voxelotor vs placebo) will be provided. A figure of the mean cumulative functions for VOC incidences for each treatment group will be presented.

In addition, for subjects ongoing in the study at the time of the dose pause, the rate of VOCs observed on-treatment and within the first 28 days after their last dose of study drug will be calculated. The rates for each time period will be standardized to 28-day rates and 95% CIs provided.

090177e1a2bf4d41\Approved\Approved On: 31-Jan-2025 17:16 (GMT)

CCI

8.2.6. Adjustment for Multiple Comparisons

To control the overall significance level (alpha) for the study at a 2-sided 5% level, a fixed sequence hierarchical test procedure will be used to formally evaluate voxelotor treatment effect in comparison to placebo at Weeks 24 and 48.

The primary and key secondary endpoints will be tested in the following order:

1. TCD flow velocity change from Baseline at Week 24 (primary endpoint)
2. TCD flow velocity change from Baseline at Week 48
3. TCD flow velocity response rate at Week 24

Each endpoint will be tested at a 2-sided alpha level of 5%. Testing of endpoints subsequent to a non-significant result will be considered exploratory in nature. Per Section 6.3 (Analysis

090177e1a2bf4d41Approved\Approved On: 31-Jan-2025 17:16 (GMT)

Timing), summaries of Week 96 or time to event efficacy endpoints based on partial data will be considered exploratory.

8.2.7. Subgroup Analyses

8.2.7.1. Change from Baseline in TCD at Week 24

Subgroup analyses will be performed to evaluate the consistency of results across pre-specified subgroups defined by demographic and baseline characteristics.

The following subgroups will be analyzed with respect to the primary efficacy endpoint (change from baseline in TCD flow velocity at Week 24):

- Age (2 to \leq 8 years; $>$ 8 to $<$ 15 years)
- Age (2 to $<$ 4 years; 4 to $<$ 12 years; 12 to $<$ 15 years)
- Sex (male; female)
- Geographic region (sub-Saharan Africa; MENA/US/UK)
- Baseline HU use (yes; no)
- Baseline TCD value (170 to $<$ 185 cm/sec; 185 to $<$ 200 cm/sec)

Subgroups by SCD genotype and race are not included as the vast majority of subjects belong to a single category (ie, HbSS for SCD genotype and African or Black/African American for race).

For the primary efficacy endpoint, a MMRM similar to that specified for the primary analysis (Section 8.2.1) will be used for each subgroup analysis based on data subset for the patient subgroup of interest. Baseline covariates included in the primary analysis but no longer relevant given the subgroup of interest will be excluded from the model.

If convergence problems with the statistical models arise due to a small number of subjects per subgroup, the analysis may be simplified by combining some of the subgroups, by excluding baseline stratification variables from the model, and/or by using a compound symmetry covariance matrix as appropriate.

The estimated treatment effects (voxelotor vs. placebo) and corresponding 95% CIs will be displayed graphically for each level of the subgroups specified.

8.2.7.2. Annualized Incidence Rate of VOC

The annualized incidence rate of VOCs will be summarized for the below subgroups and as described in Section 8.2.4. The incidence rate ratio (voxelotor vs. placebo) and corresponding 95% CIs will be displayed graphically for each level of the subgroups specified.

- Age (2 to $<$ 4 years; 4 to $<$ 12 years; 12 to $<$ 15 years)
- Sex (male; female)
- Geographic region (sub-Saharan Africa; MENA/US/UK)
- Baseline HU use (yes; no)
- Number of VOCs in past 12 months (0 events; 1 event; 2 to 10 events)

090177e1a2bf4d41Approved\Approved On: 31-Jan-2025 17:16 (GMT)

- Baseline Hb (< 7 g/dL; 7 g/dL to < 9 g/dL; ≥9 g/dL)
- Malaria TEAE on study (yes; no)

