4.2. Exclusion Criteria

Participants meeting any of the following exclusion criteria will not be eligible for study enrollment:

- 1. Body weight < 10 kg at the screening visit.
- Hospitalization for VOC or acute chest syndrome (ACS) within the 14 days prior to execution of informed consent/assent (see Section 7.2.5.1 for the definition of VOC).
- 3. More than 10 VOCs within the past 12 months that required hospitalization, emergency room, or clinic visit.
- 4. Stroke resulting in focal neurological deficit; previous silent infarcts are permitted.
- Known history or findings suggestive of significant cerebral vasculopathy (eg, moyamoya or significant vasculopathy).
- 6. History of seizure disorder.
- Has been treated with erythropoietin or other hematopoietic growth factors within 28 days of signing informed consent/assent or if, in the opinion of the Investigator, there is an anticipated need for such agents during the study.
- RBC transfusion therapy (also termed chronic, prophylactic, or preventative transfusion) or has received an RBC transfusion or exchange transfusion for any reason within 90 days of signing the informed consent/assent.
- 9. Planned initiation of HU prior to the completion of study participation.
- Severe renal dysfunction (estimated glomerular filtration rate [eGFR]< 30 mL/min/1.73 m² by Schwartz formula).
- 11. Alanine aminotransferase (ALT) > 4× upper limit of normal (ULN) for age.
- 12. History of unstable or deteriorating cardiac or pulmonary disease within 6 months prior to consent including severe or unstable pulmonary hypertension.
- 13. Clinically significant bacterial, fungal, parasitic, or viral infection currently requiring or will require therapy.
 - a. Participants with acute bacterial infection requiring antibiotic use should delay screening until the course of antibiotic therapy has been completed and the infection has resolved, in the opinion of the investigator.
- 14. Known active hepatitis A, B, or C or human immunodeficiency virus (HIV)-positive.
- Positive test indicative of active malaria infection at screening. (Malaria test to be performed only if there is suspicion of active malaria infection).
- 16. Any condition affecting drug absorption, such as major surgery involving the stomach or small intestine (prior cholecystectomy is acceptable).

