5.7.4. Other Therapies

Penicillin prophylaxis and vaccinations (including COVID-19 vaccines) are allowed in accordance with standard of care.

Other concomitant medications are allowed, unless the restrictions in Section 5.7.5 apply. Permitted concomitant medications include folic acid, L-glutamine, over-the-counter analgesics, and opioids, which are among the chronic medications commonly taken by participants with SCD.

The use of erythropoietin is prohibited during the study.
Participants who are already on malaria prophylaxis therapy may be allowed to participate in the study at the discretion of the Investigator. Participants may also be initiated on malaria prophylaxis therapy during study at the discretion of the Investigator and as per standard of care.

Participants who test positive for acute malaria during the study should be provided standard-of-care treatment and may continue in the study at the discretion of the Investigator and the Sponsor.

Participants who test positive for acute hepatitis or HIV during the study will be discontinued from study drug. An ETD visit should occur for cases when the study visit is feasible. In all cases, the participant should return for the EOS visit (28 days after the last dose of study drug).

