6.10. Eligibility Assessment, Inclusion/Exclusion Review

Eligibility assessment will be conducted during screening and prior to receiving study drug on treatment Day 1. Both at screening and prior to randomization, Investigator should determine that the participant is in stable clinical condition with Hb level near their baseline.

Randomization must occur on the same day as treatment Day 1 (the first dose of study drug). If a participant is randomized and withdrawn from the study prior to the first dose of study drug, they may not be re-screened.

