6.12.8. Malaria Screening

Malaria tests will be conducted at local laboratories in malaria-prevalent regions at screening per the Investigator's discretion, and/or at any point during the study, if there is a clinical suspicion of active infection with malaria. Participants may also be tested for malaria at screening in nonmalaria prevalent regions if deemed necessary by the Investigator. All testing will be done by a local laboratory.

Participants whose test is consistent with acute malaria at screening may be re-screened upon completion of treatment and complete resolution of malaria infection.

Participants whose test is consistent with acute malaria (active infection) while on study will be managed as per standard of care and may continue in the study at the discretion of the Investigator and the Sponsor. Cases of new onset of malaria will be reported as an AE or SAE (see Section 7 for guidance).

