Completion of study is as specified on the End of Study (EOS) CRF. Subjects are considered to have completed the study if (1) the subject completed the study through the Week 96 visit and elected to enroll in the open-label extension study, or (2) the subject did not enroll in the open-label extension study and completed the study through 96 weeks plus the EOS follow-up visit (28 days after the last dose of study drug).

[figure not shown]
Change from Baseline

Change from baseline for a given endpoint is defined as the Study Visit value minus the Baseline value.

090177e1a2bf4d41\Approved\Approved On: 31-Jan-2025 17:16 (GMT)

CCI

Treatment-emergent Adverse Event

A treatment-emergent adverse event (TEAE) is defined as an adverse event (AE) with an onset date between date of first dose and 28 days after last dose, inclusive.

090177e1a2bf4d41\Approved\Approved On: 31-Jan-2025 17:16 (GMT)

Concomitant Medications

Concomitant medications are those medications taken on or after the initiation of study drug. This definition includes medications started prior to the initiation of study drug but continue concurrently with study drug.

Prior Medications

Prior medications are those medications taken prior to date of first dose.

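### The VOC forest plot compares arms within strata defined by malaria occurring after first dose; these two ratios are not randomised comparisons and carry no caveat

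*SAP*

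**What the plan says.** SAP 8.2.7.2 lists age, sex, geographic region, baseline HU use, number of VOCs in the past 12 months, baseline Hb and, last, "Malaria TEAE on study (yes; no". All seven get the same display: "The incidence rate ratio (voxelotor vs. placebo) and corresponding 95% CIs will be displayed graphically for each level of the subgroups specified".

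SAP Section 5 defines a TEAE as an adverse event with "an onset date between date of first dose and 28 days after last dose, inclusive". Protocol 6.10 puts randomisation and first dose on the same day. Protocol 4.2 excludes children with a "Positive test indicative of active malaria infection at screening". During the study, Protocol 6.12.8 allows malaria testing "at any point during the study, if there is a clinical suspicion of active infection with malaria". Protocol 5.7.4 adds: "Participants may also be initiated on malaria prophylaxis therapy during study at the discretion of the Investigator".

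The VOC rate in SAP 8.2.4 divides events by "total subject-years on treatment", with no split at malaria onset. The VOC rate is not in the testing sequence of SAP 8.2.6. The VOC subgroup analyses entered the SAP with version 3.0 (27 Jan 2025), after dosing had been paused for a safety imbalance.

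**The concern.** A subgroup ratio inherits the protection of randomisation only if treatment cannot affect who falls into the subgroup. That holds for the six baseline factors but not for malaria status, which accrues on study. The documents leave several routes by which the arms could differ:

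- Testing follows clinical suspicion, so detection depends on the clinical course after randomisation.
- Prophylaxis may be started during the study.
- The TEAE window closes 28 days after last dose. Study drug stops on abnormal TCD (Protocol 3.1.1), and the planning assumptions expect fewer conversions on voxelotor. Time at risk of being labelled a malaria case may therefore differ by arm.

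If malaria-prone children also have a different VOC rate, each malaria row compares differently selected children. Both rows can then move the same way with no true effect on VOC, which a reader could take for a consistent finding. A reader trying to understand the VOC results after the dose pause would see these two ratios beside six of a different kind, with nothing in the SAP text to separate them.

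The split also ignores time order. A malaria TEAE late in treatment, or up to 28 days after it, moves the child's whole VOC record, including crises before the malaria, into the yes row. That limits the description but does not by itself bias the ratio between arms.

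**Working it through.** **Structure.** The plan states no figure for this panel, so there is none to reproduce. Malaria TEAE status requires onset on or after first dose (SAP Section 5), first dose falls on the day of randomisation (Protocol 6.10), and a positive test at screening excludes the child (Protocol 4.2). Status is therefore always set on or after randomisation. Neither SAP 8.2.4 nor 8.2.7.2 comments on this.

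**Size, by illustration.** These inputs are assumptions, not document figures:

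- placebo malaria hazard 0.4 per year over 1.25 years, so a = 0.4 × 1.25 = 0.5;
- a frailty u, gamma with mean 1 and variance k, multiplying both the malaria hazard and the VOC rate;
- a true VOC ratio of exactly 1 for every child.

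The probability of no malaria is L(a) = (1 + ka)^(−1/k). The mean of u carried by children without malaria is L1(a) = (1 + ka)^(−1/k − 1). The relative VOC rate is L1/L in the no row and (1 − L1)/(1 − L) in the yes row.

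For k = 1 and a malaria hazard ratio of 0.5:

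- Placebo, a = 0.5: L = 0.667 and L1 = 0.444. No row 0.667; yes row 0.556/0.333 = 1.667.
- Voxelotor, a = 0.25: L = 0.800 and L1 = 0.640. No row 0.800; yes row 0.360/0.200 = 1.800.
- Apparent ratios: 0.800/0.667 = 1.20 and 1.800/1.667 = 1.08.
- Malaria affects 33% of placebo and 20% of voxelotor children. The overall VOC ratio is 1, because u has mean 1 in both arms.

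| Malaria hazard ratio | No-malaria row, k = 1 (k = 0.5 to 2) | Malaria row, k = 1 (k = 0.5 to 2) |
|---|---|---|
| 0.5 | 1.20 (1.11 to 1.33) | 1.08 (1.05 to 1.13) |
| 0.67 | 1.13 (1.07 to 1.20) | 1.05 (1.03 to 1.08) |
| 1.0 | 1.00 | 1.00 |
| 1.5 | 0.86 (0.91 to 0.80) | 0.94 (0.96 to 0.92) |
| 2.0 | 0.75 (0.83 to 0.67) | 0.90 (0.93 to 0.87) |

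A simulation with 1,000,000 children per arm, at 0.5 per year for 1 year (again a = 0.5), gave 1.20/1.08 and 0.75/0.90 at k = 1. With no shared frailty, both rows stayed at 1.00. The overall ratio was 0.998 to 1.002 throughout.

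**Follow-up difference alone.** Here the malaria hazards are equal, and study drug stops at conversion. Planning figures: 35% conversion on placebo by Week 96 and a hazard ratio of 0.5, so 1 − 0.65^0.5 = 19% on voxelotor. The conversion hazard is −ln(0.65) = 0.431 per 96 weeks on placebo and half that on voxelotor, independent of u. With T the follow-up time and h the malaria hazard, the time-weighted rate is E[T·L1(hT)]/E[T·L(hT)] in the no row and E[T(1 − L1(hT))]/E[T(1 − L(hT))] in the yes row. At h = 0.4 per year and k = 0.5, 1 and 2:

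- 1.25 years: no row 0.993, 0.988, 0.981; yes row 0.999, 0.998, 0.996.
- 96 weeks: no row 0.986, 0.976, 0.964; yes row 0.997, 0.996, 0.993.

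The largest shift found was 6% (no row 0.944), at 0.8 per year, 96 weeks and k = 2. A much wider gap than planned, 1.0 versus 1.5 years on voxelotor and placebo, gave 1.17 (no row) and 1.06 (yes row) in the simulation. Reversed, it gave 0.86 and 0.94.

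**The case against.** The strongest reply is that bias is conditional and no passage shows the condition is met. Nothing says voxelotor changes malaria risk, the testing and prophylaxis rules apply to both arms alike, and the trial is double-blind with Hb, hematocrit, RBC count and bilirubin withheld from investigators. The only scenario tied to planning figures gives small shifts. This stands, and it is why neither direction nor size is claimed. Blinding limits differential detection, but it does not turn a status acquired on study into a baseline factor.

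The row label contains the word TEAE, and figure mock-ups sit in a separate document (SAP Section 12) that may carry a footnote. It is fair to say only that the SAP text has no caveat. A label or footnote would warn the reader but would not correct the ratios.

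All seven factors use on-treatment time and stop at HU initiation, so the baseline rows also have exposure shaped by later events. That is true, but membership of those rows is fixed before treatment, while membership of the malaria rows is not.

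Finally, the panel is exploratory, malaria is a reasonable question after a pause for a safety imbalance, and TEAE tables by preferred term and arm (SAP 8.3.3) would show an imbalance. The low stakes are accepted. The question can be answered descriptively without presenting the two ratios as subgroup treatment effects.

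**Conclusion.** The concern holds. The two malaria ratios condition on an event after randomisation, sit among six baseline subgroups, and have no caveat in the SAP text. Whether they are biased cannot be known from the documents. Bias under the null needs treatment to affect malaria occurrence, detection or time at risk, together with a link between malaria-proneness and VOC rate.

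Under the assumed shared frailty and malaria hazard ratios from 0.5 to 2.0, the apparent ratio ranges from 0.67 to 1.33 without malaria and from 0.87 to 1.13 with malaria, while the true ratio is 1. The follow-up difference implied by the planning figures adds at most 6% in the settings tried.

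The consequence is limited to reading an exploratory plot. No p-value or interaction test is planned for it, and the formal testing sequence is untouched. The change should be made, but no confirmatory conclusion depends on it.

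**What to change.** Remove the malaria row from the treatment-comparison plot in SAP 8.2.7.2. Rely on factors fixed at randomisation: the sub-Saharan Africa split already listed, or malaria-endemic country or site.

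If the link between malaria and VOC is of interest, report malaria incidence by arm and VOC rates before and after malaria onset, treating malaria as a time-dependent covariate. Label this descriptive and non-randomised, because it also conditions on an event after randomisation.

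If the panel is kept, the minimum is a footnote: *Malaria status is determined after randomisation; ratios within these strata are not randomised comparisons.*

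The cost is one line of SAP text and the loss or replacement of one exploratory panel. The before-and-after summary needs a little extra programming on adverse event dates already collected.

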8.2.8. Sensitivity Analyses

The following sensitivity analyses will be performed to evaluate the robustness of the primary efficacy endpoint results to missing data assumptions:

- WOCF: For subjects discontinued early from the study due to conversion to abnormal TCD flow velocity, missing TCD values post abnormal TCD assessment will be imputed using WOCF. All other data handling rules in Section 6.4.2.1 and the MMRM model as described in Section 8.2.1 will be applied.
- Tipping point: A tipping point analysis will be conducted by adding (or subtracting) a constant delta (or so-called shift parameter) to the post-discontinuation imputed TCD values for subjects that discontinue early due to conversion to abnormal TCD flow velocity. A separate delta will be applied to each treatment group (voxelotor and placebo) in the direction of lack of efficacy (TCD flow velocity increase for voxelotor group and TCD flow velocity decrease for the placebo group). A range of values will be used to adjust the imputed TCD flow velocity values independently for each treatment group based on a grid of delta adjustments. The resulting point estimate for the treatment effect and corresponding p-value under each pair of deltas will be tabulated. If the delta parameter needed to overturn the conclusion is so extreme that it is considered clinically implausible, then this indicates robustness to missing data assumptions.

In addition, as study drug dosing was paused prior to study termination, the following sensitivity analysis will also be performed:

- Exclusion of TCD data post dose pause: For subjects ongoing in the study at the time of the dose pause, TCD data collected after their last dose of study drug will be excluded from analysis and change from baseline in TCD assessed based on the MMRM model as described in Section 8.2.1.

8.3. Safety Analyses

Safety analysis will be performed on all subjects receiving at least one dose of study drug (Safety Population; Section 7). Adverse events will be coded using the MedDRA version at the time of the analysis data cutoff.

All safety summaries will include results up to 28 days after last dose of study drug. Data collected more than 28 days after the last dose of study drug will be excluded from table summaries. All reported adverse events will be included in the listings.

090177e1a2bf4d41Approved\Approved On: 31-Jan-2025 17:16 (GMT)

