2. INTRODUCTION

The purpose of Study GBT440-032 (C5341021) is to evaluate the effect of voxelotor on reducing the risk of stroke, as measured by transcranial doppler (TCD) flow velocity in subjects 2 to < 15 years of age with sickle cell disease (SCD) who have conditional TCD flow velocity at baseline.

This document describes the statistical methods to be used in the summary and analysis of data from Study GBT440-032. Population pharmacokinetic (PK) analyses will be described in a separate document. Descriptive statistics for **CCI** may be summarized in a separate report. Where this document differs from the study protocol, the methodology described in the SAP is considered the latest and supersedes the corresponding section(s) in the protocol.

As of 1 May 2024, study drug dosing in GBT440-032 was voluntarily paused by the Sponsor due to a safety imbalance. Study visits and other study activities continued in accordance with the protocol. Subsequently, a decision was made by the Sponsor on 25 September 2024 to terminate the study based on the totality of clinical data for Oxybryta (voxelotor) and the last subject last visit occurred subsequently.

[figure not shown]

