8.3.3. Adverse Events

AEs will be mapped to system organ class (SOC) and preferred term using the current version of Medical Dictionary for Regulatory Activities (MedDRA). AEs will be summarized according to SCD relationship.

SCD-related AEs will be summarized separately (including but not limited to sickle cell anemia with crisis, acute chest syndrome, pneumonia, priapism, dactylitis, splenic sequestration, hepatic sequestration and osteonecrosis). All other TEAEs are considered non-SCD-related TEAEs.

The total number and percentage of subjects with TEAEs will be presented by SOC and preferred term for each treatment group. TEAEs will be presented by severity. TEAEs will be tabulated presenting the SOC alphabetically, and within each system, the preferred term will be presented in decreasing order of the number of voxelotor-treated subjects who experienced each TEAE. Treatment-related AEs will be similarly presented.

The frequency of subjects who experience each TEAE or treatment-related TEAE will be determined as follows: A subject experiencing the same AE multiple times will only be counted once for the preferred term. Similarly, if a subject experiences multiple AEs within the same SOC, that subject will be counted only once for that system. If changes in the severity of an AE are recorded in the eCRF, only the most severe incidence of the AE will be counted. If a subject experiences multiple occurrences of a TEAE, only the related event or the worst severity (table dependent) will be counted for each subject within each SOC or preferred term for the summaries of treatment-related TEAEs or TEAEs by maximum severity.

Missing onset dates will be imputed as previously outlined in Section 6.4.3 as required to determine treatment-emergent events.

Listings of all AEs, TEAEs leading to discontinuation of treatment, SAEs, Grade ≥ 3 TEAEs, and deaths will be provided.

In addition, for subjects ongoing in the study at the time of the dose pause, TEAEs and SAEs that occurred during the first 28 days after the last dose of study drug will be summarized.

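### SAP 8.3 cuts every safety table at 28 days after last dose, so no visible safety table compares later deaths or SAEs by arm, although visits continued off drug after a pause for a safety imbalance

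*SAP*

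**What the plan says.** SAP 8.3 sets a general limit, "All safety summaries will include results up to 28 days after last dose of study drug", and then the exclusion: "Data collected more than 28 days after the last dose of study drug will be excluded from table summaries". Later adverse events are kept, but only in line listings: "All reported adverse events will be included in the listings". SAP 8.3.3 names those listings: "Listings of all AEs, TEAEs leading to discontinuation of treatment, SAEs, Grade ≥ 3 TEAEs, and deaths will be provided". The summary of SAP changes places the exclusion in version 3.0, dated 27 January 2025.

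The definition of a treatment-emergent event in SAP 5 has the same limit: "an onset date between date of first dose and 28 days after last dose, inclusive". Protocol 8.5 gives no upper time limit, but SAP 2 says that the SAP prevails where the two differ.

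The background is in SAP 2. From 1 May 2024, "study drug dosing in GBT440-032 was voluntarily paused by the Sponsor due to a safety imbalance". It adds: "Study visits and other study activities continued in accordance with the protocol". The sponsor decided on 25 September 2024 to terminate the study. The last visit came afterwards, on a date not given.

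Version 3.0 added two analyses for children ongoing at the pause, and both stop at day 28. SAP 8.3.3 says that "TEAEs and SAEs that occurred during the first 28 days after the last dose of study drug will be summarized", and SAP 8.2.4 gives VOC rates on treatment and in the first 28 days off drug.

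**The concern.** A 28-day window is normal for treatment-emergent tables. Here, though, the limit applies to all safety summaries, including deaths and SAEs. It was written after a pause for a safety imbalance had created an off-drug period that the design had not foreseen. A listing preserves the records but specifies no counts, denominators or comparison by arm.

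The SAP also treats this period unevenly. SAP 8.2 keeps efficacy data from children who stopped drug but stayed in assessment, and SAP 8.2.8 removes TCD values after the pause only in a sensitivity analysis. A TCD value four months after the last dose can therefore enter the efficacy model, while a death or stroke on the same day enters no safety table. At stake is whether the final report shows, by arm, what happened to children after day 28 in a study where safety led to the pause.

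**Working it through.** **1. The plan's own follow-up.** Protocol 3.1.1 gives up to 35 days of screening, 96 weeks of treatment and 28 days of follow-up after the last dose.

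35/7 + 96 + 28/7 = 5 + 96 + 4 = 105 weeks.

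This reproduces the approximately 105 weeks in Protocol 3.3. Planned follow-up after the last dose is itself 28 days, so with dosing as planned the exclusion would have removed almost nothing. It matters because of the pause.

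**2. The off-drug interval** (dates from SAP 2, taking 1 May as the start of off-drug time).

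- 1 May to 25 September 2024: 30 + 30 + 31 + 31 + 25 = 147 days.
- Inside the safety tables: 28 days.
- Outside: 147 − 28 = 119 days, or 17 weeks; 119/147 = 81%.

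Time from the decision to the last visit would add to this.

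**3. Range for follow-up per child.** Individual durations are not given, and a child who reached Week 96 soon after the pause contributes less. If mean off-drug follow-up was half the interval (assumed), it is 73.5 days, and (73.5 − 28)/73.5 = 62% is still excluded.

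**4. Subject-years.** The number ongoing at the pause is not given. Suppose N children were each followed for all 147 days. Inside the window is N × 28/365.25 and outside is N × 119/365.25.

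| Assumed N | Inside window | Outside |
|---|---|---|
| 50 | 3.8 | 16.3 |
| 100 | 7.7 | 32.6 |
| 150 | 11.5 | 48.9 |
| 224 (planned total) | 17.2 | 73.0 |

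For each assumed N these are upper bounds on time up to the decision date. They measure time outside the tables, not events missed.

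**5. Timing of the rule.** Version 3.0 is dated 271 days after the pause and 124 days after the termination decision.

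**6. Other places where a late event might appear by arm.**

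- SAP 8.1 (disposition) reports reasons for early discontinuation at any point, by treatment group. A late death might show as a reason, but the categories are not listed and SAEs would not be counted.
- SAP 6.3 says that the Week 48 analysis summarised all safety data to its cut-off. The date is not given, so whether it reached past day 28 off drug cannot be determined.
- SAP 12 puts table shells in a separate document, and one item in the version 3.0 change log is redacted. Hence the restriction to tables visible in the SAP.

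**The case against.** The strongest reply is that the cut-off matches data collection. Protocol 7.2.1 records adverse events until 28 days after the last dose, Protocol 5.7.1 ends concomitant-medication recording at the same point, and planned follow-up is 28 days. Protocol 6.11 says that recording runs throughout the study, but refers to Section 7.2 for the period. On this view, tables beyond day 28 would rest on patchy capture, and rates over full follow-up time would be biased low.

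This stands as a caution. It does not remove the point: SAP 8.3 presupposes that later data exist, and Appendix B of the protocol schedules adverse event assessment at every visit. It does mean that complete and equal capture in the two arms cannot be assumed.

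The second reply also stands in part: withdrawal effects are covered for the first 28 days, and later deaths and SAEs are listed, not suppressed.

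Three stronger readings are tempting, and the documents do not support them.

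- *The trial was terminated for the safety imbalance.* SAP 2 gives the imbalance as the reason for the dosing pause. It attributes termination to the overall clinical evidence on voxelotor.
- *Late deaths can appear in no between-arm table at all.* The disposition table might show them.
- *Follow-up after day 28 gives an unbiased randomised comparison.* Children still followed then are a post-randomisation subset. Abnormal TCD, starting hydroxyurea and chronic transfusion all led to discontinuation (Protocol 3.1.1, 5.7.2, 5.7.3), and after the pause both arms were off study drug.

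**Conclusion.** The point holds in limited form. SAP 8.3 excludes everything more than 28 days after last dose from all safety tables, and both pause-specific analyses stop at the same day. For a child followed from the pause to the termination decision, up to 119 of 147 off-drug days (81%) have no by-arm safety summary. The 81% assumes that follow-up ran for the whole interval; at half of it the share is 62%. The documents do not give the number ongoing, individual follow-up or any late event count. The size is therefore follow-up time left out of tables, with no evidence that a conclusion would change. The endpoints, the alpha control and the 28-day tables are unaffected. This is a worthwhile and inexpensive addition to the final report.

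**What to change.** 1. Keep the 28-day tables as the on-treatment view.
2. Narrow the exclusion sentence in SAP 8.3 so that it does not apply to deaths and SAEs. Possible wording: *Safety tables are limited to 28 days after last dose, except that deaths and SAEs are also tabulated by treatment group to last contact.*
3. Add one descriptive table, by arm, of deaths and SAEs (with stroke and TIA shown) from first dose to last contact. Split it into the period up to 28 days after last dose and the period beyond, and give the number of children and the follow-up time at risk in each. No testing is needed.
4. Reconcile Protocol 7.2.1, Protocol 6.11 and SAP 8.3 on the period over which adverse events were recorded, and state what was done during the pause.
5. Footnote the later period: capture may be incomplete, rates may be underestimated, and the children are a post-randomisation subset.

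The cost is one extra table from events already recorded, plus the reconciliation. The downside is that off-drug events may dilute a drug effect if pooled, which is why the periods are shown separately.
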